6.4.6 Monitoring Subjects for Adverse Events of Special Interest

Subjects will be monitored throughout the study for the occurrence of AEs and for abnormal clinical laboratory values.

LYC-30937

Clinical Protocol LYC-30937-2003

Issue Date: 30 August 2016

AEs of special interest include those that may be related to LYC-30937's mechanism of action of mitochondrial modulation and those AEs which may indicate hepatotoxicity. Investigators should be particularly mindful of these AEs, which include vomiting, abdominal pain, elevated lactate, and abnormal liver function tests indicative of possible hepatotoxicity (AST, ALT, total bilirubin, ALP, LDH). Guidance for monitoring for these AEs of special interest is outlined below:

Vomiting or Abdominal Pain:

If a subject exhibits repeated episodes of vomiting or persistent abdominal pain they must contact their investigator. They should present to the clinic as soon as possible to be evaluated for potential source of the symptom and liver function testing should be performed. The study medical monitor should be contacted. If a source is not readily identified then study drug should be withheld and the subject should continue to be evaluated for the source and managed as medically indicated. Study drug may be re-started if it has been interrupted for no more than 3 days and the source of the vomiting or abdominal pain is determined, or if these symptoms resolve, and in the clinical judgement of the investigator and study medical monitor it is safe for the subject to continue study drug. If the subject is off drug for more than 3 days the investigator should withdraw the subject from the study.

Monitoring Lactate and Liver Function:

If a subject exhibits any of the following elevations, study drug should be withheld at least until evaluation of the subject:

- ALT or AST > 8 x ULN
- ALT or AST > 5 x ULN for more than 2 weeks
- ALT or AST > 3 x ULN and total bilirubin > 2 x ULN
- ALT or AST > 3 x ULN with appearance of fatigue, nausea, vomiting, right upper quadrant pain or tenderness, fever, rash and/or eosinophilia (> 5%)
- ALP > 1.5 x ULN
- Lactate \geq 3 mmol/L
- LDH > 2 x ULN

If any of the above occur the investigator must contact the subject to request the stop taking study drug and report to the clinic as soon as possible for evaluation (do not wait for the next

LYC-30937

Clinical Protocol LYC-30937-2003

Issue Date: 30 August 2016

scheduled study visit). As dehydration and heavy physical exertion can cause elevations (eg, of blood lactate levels), the clinical lab should be repeated with the subject instructed to ensure hydration and avoid heavy physical activity. The study medical monitor should be contacted to discuss the case. If the elevation is confirmed by repeat lab and neither dehydration nor physical exertion explains the elevation, study drug must continue to be withheld. Close observation of the subject should be initiated. Repeat liver enzyme and serum bilirubin testing should be performed 2 to 3 times weekly until values return to baseline. Frequency of this retesting can decrease to once per week or less if abnormalities stabilize or the study drug has been discontinued and the subject is asymptomatic. The investigator should obtain a detailed history of symptoms, prior or concurrent diseases, concomitant drug use, alcohol use, recreational drug use, special diets, and exposure to environmental chemical agents. Evaluation should be performed to rule out acute viral hepatitis types A, B, C, D and E; autoimmune or alcoholic hepatitis; nonalcoholic steatohepatitis; hypoxic/ischemic hepatopathy; and biliary tract disease. Obtain additional tests to evaluate liver function as appropriate (eg, international normalized ratio, direct bilirubin). Consider gastroenterology or hepatology consults. If a source of the abnormal value is not readily identified the subject should continue to be evaluated for the source and managed as medically indicated. Study drug may be re-started if study drug has been interrupted for no more than 3 days and the source of the abnormal value(s) is determined, or if upon repeating the clinical lab the value returns to normal, and in the clinical judgement of the investigator and study medical monitor it is safe for the subject to continue study drug. If study drug cannot be ruled out as the cause of the abnormal value then study drug should be permanently discontinued. Additionally, if study drug is interrupted for more than 3 days, then study drug should be permanently discontinued.

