4.4.2 Exclusion Criteria

Subjects presenting with any of the following will not participate in the study:

1. Non-plaque-type psoriasis (eg, pustular, erythrodermic, and guttate psoriasis).
2. Drug-induced psoriasis (ie, new onset or current exacerbation from beta-blockers, calcium channel blockers, or lithium).
3. Spontaneously improving or rapidly deteriorating plaque psoriasis.
4. Comorbid psoriatic arthritis not amenable to treatment with nonsteroidal anti-inflammatory drugs (NSAIDs).
5. Treatment with any biologic agent for plaque psoriasis.
6. Failed 2 or more systemic treatments for plaque psoriasis.
7. Received phototherapy or prolonged sun exposure or use of tanning booth or other ultraviolet light source within 4 weeks prior to initiating screening procedures.
8. Received systemic drug therapy (non-biologic) for plaque psoriasis or any other systemic medications that could affect psoriasis or its evaluation (PASI or static IGA), including but not limited to oral or injectable corticosteroids, retinoids, sulfasalazine, within 4 weeks of initiating screening procedures.
9. Received topical medication that could affect psoriasis or its evaluation (PASI or static IGA), including but not limited to corticosteroids, retinoids, topical vitamin D derivatives, pimecrolimus, tacrolimus, calcipotriene, within 2 weeks of initiating screening procedures.
10. Received immunosuppressant agents (eg, cyclosporine, azathioprine, methotrexate) within 8 weeks of initiating screening procedures.

LYC-30937

Clinical Protocol LYC-30937-2003

Issue Date: 30 August 2016

11. Known mitochondrial disorder.
12. Any of the following laboratory abnormalities:
 - a liver function tests > 1.5 x the upper limit of normal (ULN) or direct bilirubin > 1.5 x ULN
 - b hemoglobin < 8.5 g/dL (international system units [SI]: < 85 g/L)
 - c neutrophils $< 1500/\text{mm}^3$ (SI: $< 1.5 \times 10^9/\text{L}$)
 - d white blood cell (WBC) count $< 3000/\text{mm}^3$ (SI: $< 3.0 \times 10^9/\text{L}$)
 - e platelets $< 80000/\text{mm}^3$ (SI: $80 \times 10^9/\text{L}$)
 - f serum creatinine > 1.4 mg/dL for women or > 1.6 mg/dL for men
13. Pregnancy, lactation, or a positive serum beta human chorionic gonadotropin (hCG) measured at screening. Female subjects should not be planning to become pregnant while enrolled in the study.

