14. Clinically relevant hepatic, neurological, pulmonary, dermatological, ophthalmological, gastrointestinal, endocrine, psychiatric, or other major systemic disease making implementation of the protocol or interpretation of the study difficult or that would put the subject at risk by participating in the study.
15. Current active or history of clinically significant, recurrent bacterial, viral, fungal, mycobacterial or other infections (including but not limited to tuberculosis and atypical mycobacterial disease and herpes zoster), human immunodeficiency virus (HIV), or any major episode of infection requiring hospitalization or treatment with intravenous antibiotics within 4 weeks prior to the screening visit and at any time during the screening period, up through the first dose of study drug.

Note that recurring urinary tract infections are allowed.
16. History of cancer, including solid tumors and hematological malignancies (except basal cell and in situ squamous cell carcinomas of the skin that have been adequately treated with no re-occurrence for at least 1 year prior to screening).

LYC-30937

Clinical Protocol LYC-30937-2003

Issue Date: 30 August 2016

17. History of alcohol or drug abuse within 1 year prior to randomization.
18. History of or currently active primary or secondary immunodeficiency.
19. History of treatment with an investigational agent within 30 days prior to initiating screening procedures.
20. In the opinion of the investigator, the subject is not a suitable candidate for this study. For example, a medical condition that may put the subject at increased risk, likely not to be cooperative with study procedures or with completion of the study, or the inability to communicate reliably with the investigator.

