6.4.4 Laboratory Assessments

Laboratory assessments will be performed at the time points indicated in the schedule of assessments (Table 1) and will be evaluated by a central laboratory.

The PI at the site must assess the clinical significance of all laboratory values outside the laboratory reference ranges. All laboratory abnormalities considered to be clinically significant by the PI should be repeated. Confirmed, clinically significant laboratory abnormalities should be further evaluated by the PI and captured as an AE.

Chemistry Panel Sample

The chemistry panel includes: glucose, calcium, sodium, albumin, total protein, potassium, bicarbonate, chloride, blood urea nitrogen (BUN), creatinine, lactate, lactate dehydrogenase (LDH), alanine aminotransferase (ALT), aspartate aminotransferase (AST), reflexive bilirubin (total, direct, indirect), alkaline phosphatase (ALP), cholesterol, triglycerides, creatine phosphokinase (CPK), high sensitivity C-reactive protein (hsCRP), high density lipoprotein (HDL), and low density lipoprotein (LDL).

Hematology Panel Sample

The hematology panel includes: platelets, WBCs with differential if abnormal (% and absolute counts), hematocrit, red blood cells (RBCs), hemoglobin, mean corpuscular volume (MCV), mean corpuscular hemoglobin concentration (MCHC), and mean corpuscular hemoglobin (MCH).

LYC-30937

Clinical Protocol LYC-30937-2003

Issue Date: 30 August 2016

Urine Sample (Dipstick)

The urinalysis test includes: color, appearance, specific gravity, leukocyte esterase, pH, protein, glucose, ketones, blood, and nitrates. Microscopic urinalysis will be performed on samples with abnormal blood, leukocyte esterase, protein, and nitrate. This test will be evaluated by dipstick at the central laboratory.

Childbearing Potential Evaluation and Pregnancy Tests

Serum FSH in postmenopausal female subjects and a serum hCG (pregnancy test) in premenopausal females will be evaluated at the central lab at screening.

Urine pregnancy tests for female subjects of childbearing potential will be performed at the time points indicated in the schedule of assessments (Table 1).

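### Section 6.4.6 withholds drug at lactate ≥ 3 mmol/L, but no exclusion criterion screens for that value

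*Protocol*

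**What the plan says.** Protocol 6.4.6 names elevated lactate as an adverse event of special interest, alongside vomiting, abdominal pain and "abnormal liver function tests indicative of possible hepatotoxicity (AST, ALT, total bilirubin, ALP, LDH". It then lists seven laboratory triggers under the instruction "If a subject exhibits any of the following elevations, study drug should be withheld at least until evaluation of the subject". Four concern ALT or AST, one ALP, one LDH and one lactate. The lactate trigger is an absolute value, ≥ 3 mmol/L, with no reference to the subject's own baseline.

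After a trigger, the test is repeated with attention to hydration and exertion. "If the elevation is confirmed by repeat lab and neither dehydration nor physical exertion explains the elevation, study drug must continue to be withheld". Restart is possible if the interruption has lasted no more than 3 days, the source has been found or the repeat is normal, and the investigator and medical monitor judge it safe. An interruption longer than 3 days ends treatment for good. So does the following: "If study drug cannot be ruled out as the cause of the abnormal value then study drug should be permanently discontinued".

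On entry, exclusion 12a in Protocol 4.4.2 removes subjects with "liver function tests > 1.5 x the upper limit of normal (ULN) or direct bilirubin > 1.5 x ULN". Items 12b to 12f cover hemoglobin, neutrophils, white cells, platelets and creatinine. Lactate does not appear. The criteria that could still apply are exclusion 11 ("Known mitochondrial disorder"), exclusion 14 (relevant systemic disease) and exclusion 20, which begins "In the opinion of the investigator, the subject is not a suitable candidate for this study". Section 6.4.4 adds: "The PI at the site must assess the clinical significance of all laboratory values outside the laboratory reference ranges".

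Lactate is part of the chemistry panel (Protocol Table 1, footnote e). That panel is drawn at screening and next at Week 2, with none at Visit 2 (Protocol Table 1; SAP 6.6).

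**The concern.** A laboratory value that stops treatment should normally have an entry limit at or below it. Otherwise a subject who already meets the stopping rule can be enrolled and dosed. Here the unmatched value is lactate, which the protocol singles out for special attention in a drug that modulates mitochondrial function.

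Two things are at stake:

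- **Safety.** A subject could take about two weeks of drug at a lactate level at which the protocol itself says drug should be withheld for evaluation.
- **Retention and interpretation.** A stable, pre-existing elevation could lead to permanent discontinuation without any drug effect. It could also enter the safety tables as a treatment-emergent event, in either arm of a 30-subject trial.

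**Working it through.** **Step 1. Each trigger against the entry limit.** Triggers are from Protocol 6.4.6 and entry limits from exclusion 12a. Section 4.4.2 does not define liver function tests, so the list in 6.4.6 is used.

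| Trigger (6.4.6) | Entry limit (4.4.2) | Matched? |
|---|---|---|
| ALT or AST > 8 × ULN | > 1.5 × ULN excluded | yes |
| ALT or AST > 5 × ULN for over 2 weeks | > 1.5 × ULN excluded | yes |
| ALT or AST > 3 × ULN with total bilirubin > 2 × ULN | > 1.5 × ULN excluded | yes |
| ALT or AST > 3 × ULN with symptoms | > 1.5 × ULN excluded | yes |
| ALP > 1.5 × ULN | > 1.5 × ULN excluded | yes, with no margin |
| LDH > 2 × ULN | > 1.5 × ULN excluded | yes |
| Lactate ≥ 3 mmol/L | none | no |

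Six of the seven are matched on this reading; lactate is not.

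**Step 2. Doses before the hold.** Dosing is one capsule daily from Day 1 (Protocol 5.2), taken at home on clinic days too (5.5.2). The Week 2 visit is Day 15 ± 2 (6.1). Doses by the draw therefore number 15, with a range of 15 − 2 = 13 to 15 + 2 = 17.

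**Step 3. What follows for a persistent value.** A stable elevation does not normalize on repeat, and hydration and rest do not explain it. Restart then depends on identifying a source within 3 days, with the investigator and medical monitor in agreement. Failing that, drug is permanently discontinued.

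**Step 4. How the value may be reported.** Under 6.4.4, a confirmed, clinically significant abnormality is captured as an AE. SAP 6.5 classes an AE as treatment-emergent if it starts from the first dose date to 14 days after the last dose. If the screening value was not recorded as an AE and the Week 2 value was, the event meets that date rule. The exemption in Protocol 7.1 for unworsened conditions is limited to events of the underlying disease.

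**Step 5. Power.** Inputs from Protocol 8.1: difference 36.0, SD 32.0, two-sided t-test, alpha 0.05, 20 active and 10 placebo. The noncentrality is δ = 36 / (32 × √(1/n₁ + 1/n₂)), with n₁ + n₂ − 2 degrees of freedom. Power comes from the noncentral t distribution.

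- 20 vs 10: δ = 36 / (32 × 0.3873) = 2.905, df 28, power **80.1%**. This reproduces the plan's figure of about 80%.
- 19 vs 10: δ = 36 / (32 × 0.3907) = 2.880, df 27, power **79.3%**.
- 20 vs 9: δ = 36 / (32 × 0.4014) = 2.803, df 27, power **77.1%**.

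The two lower figures apply only if the subject has no Week 12 PASI and is not replaced. SAP 5.7 analyzes observed cases without imputation, so such a subject leaves the primary analysis.

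**Step 6. How many subjects.** The documents give no prevalence of lactate ≥ 3 mmol/L at screening. Purely as assumptions, if 1%, 2%, 5% or 10% of randomized subjects had such a value, the chance of at least one among 30, 1 − (1 − p)³⁰, would be 26%, 45%, 79% or 96%. The true figure could also be zero.

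**The case against.** The strongest reply is that judgment already covers this. The screening lactate is known before randomization, the investigator must assess every out-of-range value, 6.4.6 asks investigators to be especially alert to lactate, and exclusions 14 and 20 allow refusal. The harm needs an investigator to see the value, know the hold rule and randomize anyway. This lowers the likelihood but does not close the gap. Those provisions permit exclusion without requiring it, and the protocol did not leave liver tests, blood counts or creatinine to judgment.

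The scenario is also hypothetical. The only causes of raised lactate that 6.4.6 names are dehydration and exertion, which the repeat addresses. Phase 1a found no clinically significant laboratory abnormalities (Protocol 2.4), although it enrolled healthy men only. This stands, and it is why no prevalence is claimed.

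The consequences are softer than a bare reading of the discontinuation clauses suggests. Restart within 3 days is possible, and a matching screening value would help in judging whether drug is the cause. The lactate rule stops drug without withdrawing the subject, so a Week 12 PASI may still be obtained. Withdrawn subjects may be replaced at the sponsor's discretion (4.5). All of this stands.

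Three stronger readings are tempting. A reader might infer that the protocol contradicts itself; it does not, because an entry rule and a hold rule can differ. A reader might infer that lactate is certainly the only unmatched trigger; that depends on carrying the 6.4.6 list of liver tests into 4.4.2, where the term is undefined. A reader might also extend the point to the QTc limit of 500 ms in 7.11. That adds little, since the investigator assesses the screening ECG and 7.11 provides for symptom-triggered ECGs.

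**Conclusion.** The gap is real and modest. A subject with a persistent lactate at the hold level may be randomized, dosed for about two weeks, held, and possibly taken off drug permanently for a reason unrelated to it. The documents do not support saying that this will happen, or that it threatens the trial's power. One lost Week 12 PASI costs 0.8 percentage points (80.1 − 79.3) if active or 3.0 points (80.1 − 77.1) if placebo, and both are worst cases.

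The conclusion rests on the 6.4.6 reading of liver function tests, on an elevation that persists from screening to Week 2, and on an investigator not using the discretion available. Section 7.10 on medical monitoring was not in the text available for this review, so any safeguard there is not counted. This is a cheap improvement at the low end of what is worth raising, held with medium confidence. The case for it is mainly patient safety and retention.

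**What to change.** Add one item to exclusion 12 in Protocol 4.4.2: screening lactate ≥ 3 mmol/L, confirmed on the single repeat that 6.2.1 already allows, with that repeat taken after adequate hydration and without heavy exertion, as 6.4.6 asks.

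The cost is a short amendment and an occasional repeat sample or screen failure. No new scheduled test is needed, because lactate is already in the screening panel. Screening may precede dosing by up to 14 days, so the rule removes persistent elevations but does not guarantee the Day 1 value.

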7.0 ADVERSE EVENTS AND SAFETY MONITORING

7.1 Adverse Event Definition

Defined by 21 Code of Federal Regulation (CFR) 312.32(a) and consistent with International Council on Harmonization (ICH) E2A guidance, an AE means untoward medical occurrence associated with the use of a drug in humans, whether or not considered drug related. An AE can be any unfavorable or unintended sign (eg, an abnormal laboratory finding), symptom, or disease temporally associated with the use of a drug, without any judgment about causality. Examples of AEs include but are not limited to:

- abnormal test findings

LYC-30937

Clinical Protocol LYC-30937-2003

Issue Date: 30 August 2016

- clinically significant symptoms and signs
- changes in PE findings
- hypersensitivity
- progression/worsening of underlying disease

Events related to the underlying disease(s), which have not worsened in intensity (severity) or frequency since screening, are not AEs.

7.2 Serious Adverse Events Definition

Defined by 21CFR 312.32(a) and consistent with ICH E2A guidance, an AE is considered “serious” if, in the view of either the investigator or Sponsor, it results in any of the following outcomes:

- death
- life-threatening (ie, in the view of either the investigator or sponsor, its occurrence places the subject at immediate risk of death. It does NOT include an event, that had it occurred in a more severe form, might have caused death.)
- in-subject hospitalization or prolongation of existing hospitalization
- persistent or significant incapacity or substantial disruption of the ability to conduct normal life functions
- congenital anomaly/birth defect
- other medically significant events that, based upon appropriate medical judgment, may jeopardize the subject and may require medical or surgical intervention to prevent one of the outcomes listed above (eg, an allergic bronchospasm requiring intensive treatment in an emergency room or home, blood dyscrasias or convulsions that do not result in hospitalization, or the development of drug dependency)

7.3 Adverse Event Reporting

Adverse events, both serious and non-serious, should be collected on source documents from the time the subject has signed informed consent through last subject visit. The investigator is to

LYC-30937

Clinical Protocol LYC-30937-2003

Issue Date: 30 August 2016

collect all directly observed AEs and all AEs spontaneously reported by the study subject. In addition, each study subject will be questioned about AEs. For all enrolled/randomized subjects, AEs should be recorded on CRFs from the time the subject has signed informed consent. For subjects not randomized, only SAEs and AEs leading to screen failure will be collected on the CRFs from the time the subject has signed informed consent.

Each AE is to be assessed to determine if it meets the criteria for SAE, see Section 7.2 above. If an SAE occurs, expedited reporting will follow local and international regulations, as appropriate.

AEs should be reported using concise medical terminology on the CRFs. The diagnosis should be recorded on the CRF, rather than recording individual signs and symptoms. For example, congestive heart failure should be recorded rather than low ejection fraction, pedal edema, rales and dyspnea. However, if a diagnosis is known and there are other signs or symptoms that are not generally part of the diagnosis, the diagnosis and each sign or symptom not part of the diagnosis should be recorded separately, for example: congestive heart failure and conjunctivitis should be recorded as separate AEs.

Diagnostic and therapeutic noninvasive procedures should not be reported as AEs. However, the medical condition for which the procedure was performed should be reported if it meets the definition of an AE and procedure would be the treatment and recorded as “action taken” of the AE.

For all AEs, the investigator must pursue and obtain information adequate both to determine the outcome of the AE and to assess whether it meets the criteria for classification as an SAE requiring immediate notification to Lycera or its designated representative. For all AEs, sufficient information should be obtained to determine the causality of the AE.

All AEs that occur from the time of informed consent, regardless of whether the particular event is expected and regardless of relatedness, will be recorded as an AE.

